Breathing intervention (AIH or SHAM): Breathing interventions will begin 30 min after caffeine or placebo to approximately coincide with peak plasma caffeine concentrations.³⁰ Participants will don a latex-free, full non-rebreather mask with a custom neoprene head strap while they sit comfortably in a semi-reclined chair. Intermittent gas mixtures will be delivered via automatic adjustment of one-way valves attached to a hypoxia generator [HYP123, Hypoxico Inc., USA].³¹ We will deliver preset air mixtures of $\text{FIO}_2=0.09\pm 0.02$ (hypoxia) or $\text{FIO}_2=0.21\pm 0.02$ (normoxia) for 1.5min at 1 min intervals of room air breathing. The generator will fill reservoir bags attached to a non-rebreathing facemask worn by subjects. Oxygen concentration will be continuously monitored [OM-25RME; Maxtec Inc, USA]. We will take precautions to ensure safety during interventions by monitoring 5-lead electrocardiography (ECG) and recording oxyhemoglobin saturation via pulse oximetry (SpO_2) and heart rate (HR) at 2-second intervals. Respiratory rate (RR) and blood pressure (BP) will be recorded every 5th breathing interval [Dash 4000 Patient Monitor, GE]. We also will record SpO_2 , HR, RR, and BP at the start and end of walking practice and again at the end of each treatment session.

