Safety considerations for AIH: The physiological effects of AIH in humans are well studied and the methods proposed here deemed safe. Daily AIH-induced enhancements in breathing capacity, limb strength, and walking function occurred without significant adverse events in humans with chronic SCI.³²⁻³⁴ Although prolonged chronic exposure to more severe and longer duration hypoxia causes serious morbidity,³⁵ considerable data show that repetitive exposure to brief mild AIH elicits meaningful functional benefits without pathology.^{8, 36, 37} With mild AIH, the severity of hypoxemia, number of episodes, and exposure duration are low (15 episodes per day, 5 days) versus the chronic hypoxia experienced in obstructive sleep apnea (80-400 episodes per day for years^{35, 38}). Daily AIH (10 episodes/day, 7 days) showed no evidence for hypertension or weight loss⁹ or hippocampal gliosis or cell death in rats with SCI.⁸ Prior study in persons with SCI found no adverse events associated with mild exposures of single-day and dAIH (5 days), and all subjects tolerated exposures well.^{32, 33} No changes in mean arterial blood pressure or heart rate were found before and after each treatment or between baseline and the end of the exposure week. No maladaptive changes in cognitive or spasticity were found either, as measured by the Mini-Mental State Examination and Spinal Cord Assessment Tool for Spasticity.

We have taken great care and consideration in establishing a safe AIH protocol for persons with SCI. Rodent studies were developed using modest protocols of dAIH (10, 5 min episodes; 7 days^{8, 9}). In humans, we selected even more modest dosing (15, 1.5 min episodes; up to 5 days).^{32, 33} Our mild AIH dose of 1.5-min duration is based on human studies that delivered short doses of hypoxia ($\text{SaO}_2=80-85\%$) without report of adverse events.^{32, 33, 39, 40} We also based our AIH protocol on the pattern-sensitive effects of dAIH on respiratory motor control that were more dependent on the intermittency and repetition than the duration of the

DETAILED STUDY PROTOCOL

episodes.^{5, 7, 41-43} Such pattern-sensitivity is common to many models of neuroplasticity⁴⁴ including serotonin-dependent plasticity.⁴⁵ Daily exposures in rats (7 days) allowed for further amplification of the gains without eliciting maladaptive changes, such as cell death, hypertension, or weight loss.^{8,9}

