We will quantify overground walking ability using the 10MWT.⁴⁹ Subjects will perform 2 trials each of the 10MWT at their fastest but safe speed with a minimum of 1-minute rest between trials. Average speed across the two 10MWT trials will be used for analyses. The validated assessment tool will provide an indication of return of our subject population to pre-morbid activities following the initial neurological insult. The 10MWT has high inter-rater reliability, and the rating procedure can be accomplished in approximately 30 minutes.

The screening and physical assessment procedures will last approximately 1.5 hours.

To ensure safety, we also will assess pain, spasticity, systemic hypertension, and autonomic dysreflexia prior to and following caffeine and AIH interventions. We routinely measure pain, spasticity, and incidence of hypertension and autonomic dysreflexia as part of our study protocols in persons with chronic SCI.^{32, 33} We will make measurements at baseline, after session 5, and one-week follow-up, and again at two-weeks follow-ups.

Quantify pain: We will assess pain severity using the Wong-Baker FACES scale of 0 (no pain) to 5 (extreme pain).^{59, 60}

DETAILED STUDY PROTOCOL

Quantify spasticity: We will assess spasticity using the Spinal Cord Assessment Tool for Spastic Reflexes (SCATS).⁵⁸ We will quantify total lower extremity spasticity score using the cumulative sum of 3 SCATS subscales: clonus (0=no spasticity; 3=severe), flexor (0=no spasticity; 3=severe), and extensor (0=no spasticity; 3=severe).

Quantify systemic hypertension incidence rate: In addition to monitoring during the intervention, we will measure systolic and diastolic BP at baseline, after sessions 5, and again at follow-ups. We will define a systemic hypertensive event as a systolic pressure exceeding 140 mmHg and/or diastolic pressure exceeding 90 mmHg.^{46, 47}

We will compute hypertension incident rate for each intervention group as the number of hypertensive events divided by the total person-time. We define person-time in units of person-measures (the sum of the total number of BP measurements) taken for each person. Person-measures accounts for the total number of chances for detecting a hypertensive event and accounts for measurements not made due to drop-out or a disqualifying adverse event.⁶³ Finally, we will compute Relative Risk for each Aim as the incidence rate in the dAIH groups over the incidence rate in the dSHAM groups.⁶⁴

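### The hypertension incidence rate has no at-risk window: pre-exposure baseline readings count as events of that round's intervention and, if background events occur, pull the AIH/sham relative risk toward 1

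*Combined protocol and SAP*

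**What the plan says.** Protocol section 18, under the hypertension incidence rate, sets out the measure in four steps.

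- Readings: "In addition to monitoring during the intervention, we will measure systolic and diastolic BP at baseline, after sessions 5, and again at follow-ups".
- Event: "We will define a systemic hypertensive event as a systolic pressure exceeding 140 mmHg and/or diastolic pressure exceeding 90 mmHg". This is an absolute threshold with no required rise from baseline.
- Rate: "We will compute hypertension incident rate for each intervention group as the number of hypertensive events divided by the total person-time", where "We define person-time in units of person-measures (the sum of the total number of BP measurements) taken for each person".
- Contrast: "we will compute Relative Risk for each Aim as the incidence rate in the dAIH groups over the incidence rate in the dSHAM groups".

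Protocol sections 11a and 13 place the baseline up to 3 days before the first treatment of a round. Table 1 schedules blood pressure on days 0, 1 to 5, 8 and 14. Within sessions, section 11a says "blood pressure (BP) will be recorded every 5th breathing interval", and adds readings at the start and end of walking practice and at the end of the session. Section 18 does not say which of these in-session readings are person-measures.

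SAP section 13 repeats the event definition. The SAP contains no incidence-rate or relative-risk analysis, so it does not settle the point.

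**The concern.** A reading taken before the round's first capsule and first hypoxia exposure cannot show an effect of that round's intervention. As written, it still enters the denominator and, if above 140/90, the numerator. Section 18 says that finding out whether the combined protocol brings on hypertension is essential to establishing safe delivery, and a pre-exposure reading carries no information about onset. For autonomic dysreflexia the same section uses baseline as the reference for a rise in systolic pressure; for hypertension it pools baseline into the rate.

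Background events appear at a similar rate in every condition, so they move the ratio toward 1. For a harm comparison that is the non-conservative direction. A second gap makes it worse: the set of eligible in-session readings is not fixed, and the amount of dilution depends on it, so the choice could be made after the data are seen.

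**Working it through.** The plan states no hypertension rate, relative risk or power for this endpoint, so there is no figure of its own to reproduce. The reading counts below follow from the protocol; all event rates are assumptions.

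**Readings per participant per round**

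- Off-session: 1 baseline and 2 follow-ups (section 18, Table 1).
- During breathing: "15 episodes per day, 5 days" with a reading every 5th interval gives 15/5 = 3 per session, and 3 × 5 = 15 per round.
- Around walking practice and session end: 3 per session, 3 × 5 = 15 per round.
- After session 5: 1.

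**Four possible sets of person-measures**

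- A: only the four occasions listed in section 18 (1 on-session, 3 off-session).
- B: one reading per Table 1 visit (5 on, 3 off).
- C: the four occasions plus every-5th-interval readings (16 on, 3 off).
- D: C plus walking-practice and end-of-session readings (31 on, 3 off).

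**Formula.** Let p_s be the share of sham on-session readings above 140/90, p_b the share among unexposed readings, and RR the true on-session relative risk. With the same schedule in every condition,

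RR_obs = (n_on × RR × p_s + n_off × p_b) / (n_on × p_s + n_off × p_b).

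If p_b = p_s, this reduces to 1 + w(RR − 1), where w is the share of readings that can carry the effect. If the effect persists to days 8 and 14, the two follow-ups move to the exposed side and only baseline dilutes.

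**Results for true RR = 2.0 and p_s = p_b = 5%**

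| Set | Off-session share | Baseline and follow-ups dilute | Only baseline dilutes |
|---|---|---|---|
| A | 3/4 = 75% | (0.10 + 0.15)/0.20 = 1.25 | (0.30 + 0.05)/0.20 = 1.75 |
| B | 3/8 = 37.5% | (0.50 + 0.15)/0.40 = 1.63 | (0.70 + 0.05)/0.40 = 1.88 |
| C | 3/19 = 15.8% | (1.60 + 0.15)/0.95 = 1.84 | (1.80 + 0.05)/0.95 = 1.95 |
| D | 3/34 = 8.8% | (3.10 + 0.15)/1.70 = 1.91 | (3.30 + 0.05)/1.70 = 1.97 |

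**Sensitivity to the background rate (true RR 2.0, p_s = 5%, baseline and follow-ups dilute)**

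- p_b = 1%: A gives (0.10 + 0.03)/(0.05 + 0.03) = 1.63; D gives (3.10 + 0.03)/(1.55 + 0.03) = 1.98.
- p_b = 0: the n_off terms vanish and RR_obs = 2.00 in every set.

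**Sensitivity to the true effect (p_s = p_b = 5%, baseline and follow-ups dilute).** True RR 1.5: A gives 1.13 and D gives 1.46. True RR 3.0: A gives 1.50 and D gives 2.82.

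**The case against.** Several points on the other side have force.

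- **Dilution is not automatic.** A reader might infer that any blood pressure effect is diluted. The documents do not support that: with equal schedules and no background events the ratio is unchanged, and section 10 excludes people with hypertension. This stands as a limit on size. It does not make zero background safe to assume, because section 11d anticipates medication for systemic hypertension among participants.
- **Follow-ups are not shown to be unexposed.** One might argue that days 8 and 14, being 3 and 9 days after day 5, lie at least 10 caffeine half-lives past the last dose (72 h / 7 h ≈ 10). But the stated contrast is AIH against sham, and the only sham condition also receives caffeine. Caffeine elimination says nothing about how long an AIH effect on blood pressure lasts. The objection stands, and it is a reason to keep follow-up readings in the safety report.
- **The large figures need a narrow reading.** A fall from 3.0 to 1.5, or from 2.0 to 1.25, requires that only four occasions count. Section 18 lists those occasions in addition to in-session monitoring, and a total of all measurements more naturally includes the readings in section 11a. Dilution is then modest.
- **The crossover balances baselines.** Each participant has a baseline in every condition, so a chronically high reading tends to appear on both sides. That limits false excess in one condition, but equal background on both sides is exactly what draws a ratio toward 1.
- **No decision rests on the ratio.** No test or stopping rule uses it, and participants are protected by monitoring during sessions. This keeps the point below critical.

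**Conclusion.** The point holds in a bounded form. The stated rule pools pre-exposure readings into a safety rate whose purpose is to detect onset, and nothing in the protocol or SAP removes them. The resulting bias is toward a relative risk of 1 whenever background events occur.

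Its size depends on assumed event rates and on an unspecified set of readings. On the more natural reading, with in-session measurements counted, a true relative risk of 2.0 would be reported as about 1.84 to 1.91 at a 5% background and sham rate if follow-ups also dilute, and 1.95 to 1.97 if only baseline does. The fall to 1.25 applies only if nothing but the four listed occasions counts and the effect has gone by day 8. At zero background with equal schedules there is no bias. The documents support neither a claim that every effect is diluted nor the removal of follow-up readings from the safety comparison. The change is worth making because it corrects a stated rule, fixes an open analysis choice and uses data already scheduled.

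**What to change.** In Protocol section 18, and in a matching SAP entry since the SAP now has none:

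1. Exclude each round's baseline readings (before the first capsule of that round) from the numerator and denominator, and use them only as the reference.
2. State that the in-session readings of section 11a count as person-measures.
3. Report on-treatment (D1 to D5) and follow-up (F1, F2) rates and relative risks separately, and keep both in the safety report so that a persisting effect stays visible.

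This is a wording change, to be made before analysis, with no added measurements. The cost is precision: each rate rests on fewer readings. Under set D, for example, the 34 pooled readings per round become 31 on-treatment and 2 follow-up readings, with 1 baseline reading as reference. The follow-up rate, with two readings per participant per round, will be imprecise and should be read as descriptive.

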Quantify autonomic dysreflexia incidence rate: We will assess the occurrence of autonomic dysreflexia in all intervention groups. Systolic blood pressure (SBP) will be measured as detailed in common methods. We will assess SBP at baseline, and before, during and immediately after breathing interventions, and again at follow-ups. Additional SBP measurements will be made if participants first present with symptoms characteristic of autonomic dysreflexia (e.g., headache, diaphoresis, blurred vision). An autonomic dysreflexia event will constitute a participant having a SBP increase from baseline of 20 mmHg or SBP greater than 150 mmHg with complaints of headache, diaphoresis, and/or blurred vision and will be diagnosed by our study team clinicians (physicians and physical therapists). An autonomic dysreflexia event will result in termination of study participation and require prompt evaluation by the team physicians and emergency medical team.

We will compute autonomic dysreflexia incident rate for each group as the number of autonomic dysreflexia events divided by the total person-time. We define person-time in units of person-days (the number of days a person remains in the study). Person-days accounts for the total number of chances for detecting autonomic dysreflexia and accounts for days on which measurements were not made due to drop-out or a disqualifying adverse event.⁶³ Finally, we will compute Relative Risk as the ratio of incidence rates between groups.⁶⁴

We previously demonstrated that daily exposures of AIH (up to 5 consecutive days) do not elicit adverse clinical events in persons with chronic SCI.^{32, 33} Similarly, rodents exposed to daily exposure for 7 consecutive days did not induce hippocampal cell death, changes in body mass, or hypertension,^{8, 9} including in animals early after injury.⁸ Determining whether dAIH or in combination protocols lead to the onset of significant pathology (pain, spasms, hypertension, autonomic dysreflexia) in persons with SCI is essential for establishing safe delivery of caffeine combined with AIH in this earlier stage of injury.

Quantify inflammation: We will quantify inflammation using measures of C-reactive protein concentrations in the blood.

- Participant retention plans: Whether or not you complete the whole study, we will pay you \$25 for each visit you do complete. We will also reimburse for up to \$100 per visit in travel

DETAILED STUDY PROTOCOL

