• Blinding Questionnaire		x	x	x	x	x			
• Weight (kg)	x						x	x	
Safety Outcomes									
• Pain (0-10)	x	x	x	x	x	x	x	x	
• Blood pressure (mmHg)	x	x	x	x	x	x	x	x	
• Heart rate (BPM)	x	x	x	x	x	x	x	x	
• Oxygen saturation (%)	x	x	x	x	x	x	x	x	
• Memory (0-30)	x	x	x	x	x	x	x	x	
Biomarkers									
• CYP1A2 Polymorphism	x								
• Caffeine serum level (mg/L)		x				x			
• Inflammation (CRP)		x			x		x		

IV. Statistical Principles

We plan to use a parametric linear mixed model since this method is sensitive to within subject changes and robust against variability, small sample sizes, and missing/unbalanced data sets as compared to other statistical models.²⁶ If the results do not meet these model assumptions, we will apply alternative non-parametric tests.

16. Level of significance

All applicable statistical tests will be 2-sided and will be performed using a 5% significance level.

17. Adjustment for multiplicity

we do not plan to adjust for multiplicity.

18. Confidence intervals

Statistical comparisons will include 95% (2-sided) confidence intervals (CIs).

19. Adherence and protocol deviations

We will record a deviation (if the even does not significantly affect a participant's rights, safety, or well-being, or trial outcomes), or a violation (if the deviation may potentially significantly impact the completeness, accuracy, and/or reliability of the trial data or that may significantly affect a patient's rights, safety, or well-being). All protocol deviations/violations will be logged, but no formal statistical testing will be performed.

Adverse events will be reported on an IRB-approved electronic Case Report Form (eCRF). Details will include the type of event, date of onset, duration, intensity, causality relationship to the study drug(s), and outcome. If an adverse event should occur, every attempt will be made to obtain as much information as possible about event evaluation and outcome. If a serious adverse event occurs, the treatment will be interrupted or discontinued at the physician investigator's discretion. All protocol deviations will be reported to the PI ([name]) and the IRB.

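### The hypertension Relative Risk counts single BP readings from about 20 people who appear on both sides of the ratio, and no stated variance method allows for either

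*Combined protocol and SAP*

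**What the plan says.** Protocol section 18 (systemic hypertension incidence rate) defines an event as a "systolic pressure exceeding 140 mmHg and/or diastolic pressure exceeding 90 mmHg". It continues: "We will compute hypertension incident rate for each intervention group as the number of hypertensive events divided by the total person-time". The unit of person-time is the single reading: "We define person-time in units of person-measures (the sum of the total number of BP measurements) taken for each person". The effect measure follows: the team will "compute Relative Risk for each Aim as the incidence rate in the dAIH groups over the incidence rate in the dSHAM groups", with a reference that the protocol lists under a title about confidence intervals for relative risks and rates.

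SAP 18 promises two-sided 95% intervals for statistical comparisons. The design is a three-round cross-over (protocol section 11a) in which every participant is planned to have two AIH rounds and one SHAM round.

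Neither document says how the variance of this ratio will be computed. Subject as a random effect is specified only for walking speed (protocol section 20, SAP 27). SAP 30 (Harms) contains no blood pressure analysis, and SAP 29 foresees no further methods.

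**The concern.** A rate per reading, pooled over people, gives a person with 30 readings the weight of 30 separate observations. Readings taken minutes apart in one person during one round are likely to be alike, so the information is nearer to the number of people than to the number of readings. In addition, the dAIH and dSHAM rates come from the same participants. An ordinary interval for a ratio of two person-time rates allows for neither feature.

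Protocol section 18 itself treats the question of whether these interventions bring on hypertension as essential to establishing safe delivery. A ratio and interval that one or two of 20 people can decide would be a weak basis for an answer in either direction.

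**Working it through.** The documents give no rate, event count or interval for this ratio, so there is no stated figure to reproduce. The steps below rebuild the number of readings and then test how a standard interval would behave.

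**1. Readings per person per round.**
- Sessions: "15 episodes per day, 5 days" (section 11a, safety considerations for AIH).
- During breathing: "blood pressure (BP) will be recorded every 5th breathing interval", so 15 / 5 = 3 per session.
- Start of walking practice, end of walking practice, end of session (section 11a): 3 per session.
- Baseline and two follow-ups (section 18): 3 per round.

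Total: (3 + 3) × 5 + 3 = 33. For 20 people this is 20 × 33 = 660 SHAM readings and 2 × 660 = 1,320 AIH readings.

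Other readings of the text give 34 (reading after session 5 counted separately), 48 (room-air intervals also counted as breathing intervals), 8 (one per visit in Table 1) or 4 (only baseline, after session 5 and two follow-ups).

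**2. Direction of the error.** Let m be the readings per round, ρw the correlation between readings in the same round, and ρb the correlation between readings in different rounds of one person. With a common single-reading variance, in units of that variance and per person:
- variance of one round's mean: v = (1 + (m − 1)ρw) / m
- variance of (mean of two AIH rounds − SHAM mean): v + (v + ρb)/2 − 2ρb = 1.5(v − ρb)
- variance if all readings were independent: 1/m + 1/(2m) = 1.5/m

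Ratio of correct to independent variance: m(v − ρb) = 1 + (m − 1)ρw − mρb.

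With m = 33 and ρw = 0.3 (assumed):

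| ρb | Variance ratio | Correct SE / independent SE |
|---|---|---|
| 0 | 10.6 | 3.26 |
| 0.15 | 5.65 | 2.38 |
| 0.25 | 2.35 | 1.53 |
| 0.30 | 0.70 | 0.84 |

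The two effects cancel at ρb = 32 × 0.3 / 33 = 0.29. Below that the independent interval is too narrow; above it, slightly too wide. With ρw = 0.3 and ρb = 0.15, m = 4 gives 1 + 0.9 − 0.6 = 1.3 (SE × 1.14) and m = 8 gives 1 + 2.1 − 1.2 = 1.9 (SE × 1.38).

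**3. Simulated coverage.** The interval tested was log ratio ± 1.96 × √(1/a + 1/s), where a and s are the AIH and SHAM event counts. Settings: true ratio 1, N = 20, two AIH rounds and one SHAM round, 5% event rate, 4,000 runs, every high reading an event. SDs are on the logit scale and are assumed. Runs with no events on one side were dropped (at most 5.6%, at 4 readings).

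| Person SD | Person-by-round SD | 33 readings | 8 readings | 4 readings |
|---|---|---|---|---|
| 0 | 0 | 96% | 97% | 98% |
| 1.5 | 0 | 97% | 98% | 99% |
| 1.5 | 0.5 | 89% | not run | not run |
| 1.5 | 1.0 | 73% | 93% | 97% |
| 1.5 | 1.5 | 60% | 88% | 95% |

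A second set of assumptions (logit mean −4, person SD 2, 33 readings) gave 97%, 90%, 72% and 59% at person-by-round SD 0, 0.5, 1.0 and 1.5. When readings in a round were counted only up to the first event, that same model gave 99%, 99%, 98% and 97%.

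**4. Influence of one person** (illustrative counts).
- 40/1,320 against 20/660: ratio 1.00; SE of the log = √(1/40 + 1/20) = 0.274; interval 0.58 to 1.71.
- One participant now has 15 further high readings in each AIH round. The count becomes 40 + 30 = 70 and the denominators do not change. Ratio 1.75; SE = √(1/70 + 1/20) = 0.254; interval 1.06 to 2.88.

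One person in 20 turns a ratio of 1 into one whose interval excludes 1. In the simulations with 33 readings, a 5% event rate and person SD 1.5, three of the 20 people supplied 57 to 59% of all events on average, against 25% without clustering.

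**The case against.** Five points can be made for the plan.

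- **No interval formula is written down.** Section 18 stops at the ratio, the cited reference is known here by title only, and SAP 18 is a general sentence. This stands: the documents do not support saying that the plan's interval is wrong. They support saying that no method is stated that handles clustering and pairing, and that the usual method would not.
- **Repeat events may be rare.** Hypertension is an exclusion criterion, and sections 11b and SAP 13 prepare the team to discontinue treatment after a hypertensive event under the same definition. If this leaves at most one event per person-round, the loss of coverage disappears. But the documents do not say whether repeated high readings are one event or several.
- **The count of 33 is derived.** Section 18 separates monitoring during the intervention from the listed measurements, and at 4 readings little is lost. However, the denominator is the total number of BP measurements, with no limit to the listed ones.
- **Symptom-triggered readings.** A reader might infer from "Additional SBP measurements will be made if participants first present with symptoms characteristic of autonomic dysreflexia" that such readings inflate the hypertension rate. The documents do not say so: that sentence concerns autonomic dysreflexia, covers systolic pressure only, and belongs to a rate per person-day. It is at most an ambiguity.
- **Nothing is decided on this ratio.** Trial stopping under SAP 13 depends on serious adverse events directly attributed to the interventions. This stands and limits the consequence to interpretation of safety.

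**Conclusion.** The concern holds in a limited form. The reading is the unit, about 20 people supply all readings, the same people are on both sides of the ratio, and no variance method allows for either. A standard person-time interval would be miscalibrated, and one participant with repeated high readings could drive the result.

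It is tempting to conclude that the interval will be falsely narrow. The documents do not establish this, because they give no correlation, no event rate, no rule for repeat events and no explicit count of readings. With a constant personal tendency the standard interval is slightly conservative (about 97%). It becomes too narrow if the tendency varies between rounds and each high reading is an event: down to about 59% at 33 readings and the largest SD assumed, about 88% at 8 readings, and 95% or more at 4. If only first events count, coverage is 97 to 99%. Too narrow is the likelier error if many in-session readings count, because readings minutes apart are plausibly more alike than readings weeks apart.

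**What to change.** In protocol section 18, with a matching entry in the SAP:
1. State which scheduled readings enter the hypertension rate, and whether repeated high readings in one person are one event or several for the analysis.
2. Summarise each participant-round in two ways: any event (yes/no), and the share of scheduled readings above the threshold.
3. Compare interventions within participant, with a 95% interval from a bootstrap that resamples whole participants. Alternatively, use a GEE clustered on participant (log-linear for counts, with log number of readings as offset) and a small-sample correction, since there are at most 20 clusters.
4. List any symptom-triggered readings separately from the rate.

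The cost is wording and a little analysis work. No new data are needed and no clinical rule changes. The downside is that the interval may be wider.

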Our study coordinator, study physicians, physical therapists, PI ([name]), and research collaborators recruited subjects using a variety of strategies shown effective in the past. First, the team identified potential subjects using Institutional Review Board (IRB) approved resources to inform persons with SCI that are currently admitted to inpatient rehabilitation/outpatient units of Spaulding Rehabilitation Hospital, Boston University Medical Center, Massachusetts General Hospital, Gaylord hospital, Albany Medical Center, and Maine Medical Center. Subjects also will be recruited by word of mouth and flyers at these facilities. Eligible subjects screened at INSPIRE Laboratory, Spaulding Rehabilitation Hospital Cambridge, MA. At the screening visit, subjects informed of this project, their potential involvement, the possible benefits, and risks, and their right to terminate participation at any time without penalty. Qualifying subjects in agreement with the study details asked to sign the informed consent and HIPAA form approved by Partners IRB. All potential subjects entered the study according to the inclusion/exclusion criteria above and following medical clearance. Experiments will be conducted at the Spaulding Rehabilitation Hospitals.

11. Interventions

- a. Intervention Procedures: This placebo-controlled study will examine the combined effects of caffeine (vs. placebo) and AIH (vs. SHAM) on walking performance in persons with chronic, iSCI. Participants will receive three combinatorial interventions in random order: placebo+AIH, caffeine+AIH, caffeine+SHAM. The order of interventions will be block randomized. The initial screening and evaluation procedures are similar for all participants. For each intervention, participants will complete up to 8 visits/intervention (1 baseline/intervention + 5 treatment days/intervention + 2 follow-up days/intervention). Participants will complete a total of 24 visits (8 visits/intervention x 3 interventions) after the initial screen. Participant enrollment and allocation will be completed during the screening visit. Baseline will be recorded up to 3 days prior to the first intervention.

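### The hypertension incidence rate, as written, counts the pre-treatment baseline reading of each round; count from the first capsule instead (minor effect)

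*Combined protocol and SAP*

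**What the plan says.** The rule is in Protocol 18, under the heading on the systemic hypertension incidence rate. The occasions are given as: "In addition to monitoring during the intervention, we will measure systolic and diastolic BP at baseline, after sessions 5, and again at follow-ups". An event is a systolic pressure above 140 mmHg and/or a diastolic pressure above 90 mmHg, with no requirement that it be new or follow a dose. The rate for each intervention is events over person-time, and for person-time the text says: "We define person-time in units of person-measures (the sum of the total number of BP measurements) taken for each person". The reason given is that "Person-measures accounts for the total number of chances for detecting a hypertensive event". The relative risk is the rate under dAIH over the rate under dSHAM.

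Protocol 11a sets the visits as "1 baseline/intervention + 5 treatment days/intervention + 2 follow-up days/intervention" and states: "Baseline will be recorded up to 3 days prior to the first intervention". Every round therefore has its own pre-treatment baseline visit.

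Later in Protocol 18, the purpose of the safety outcomes is given as learning whether the interventions "lead to the onset of significant pathology (pain, spasms, hypertension, autonomic dysreflexia").

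SAP 13 repeats the 140/90 threshold, and SAP 30 deals with harms. Neither gives a narrower rule for this rate.

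**The concern.** Read plainly, the baseline reading of each round counts in the denominator and, if high, also in the numerator. It is credited to an intervention that has not yet been given. That does not fit a stated interest in onset. The autonomic dysreflexia rule in the same section does use baseline as a reference, through a 20 mmHg rise in systolic pressure; the hypertension rule has no such anchor.

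A reading with no treatment effect adds the same expected amount to both sides of the dAIH/dSHAM comparison. If some baseline readings are high, the ratio is pulled towards 1, which for a safety measure is the reassuring direction. If none are high, the ratio stays as it is and each rate is understated.

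A related gap is that the text does not say outright whether readings taken during sessions count. Its opening words about monitoring most naturally bring them in. The answer decides how much weight the baseline reading carries.

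**Working it through.** The plan states no hypertension rate, ratio or power for this measure, so there is no figure to reproduce. The check is how far the baseline reading can move the ratio.

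**Readings per round (n), three ways to count**

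- *All recorded readings.* Protocol 11a says "Respiratory rate (RR) and blood pressure (BP) will be recorded every 5th breathing interval"; with 15 episodes per session that is 15/5 = 3. It adds "BP at the start and end of walking practice and again at the end of each treatment session", which is 3 more. Five sessions give 5 × (3 + 3) = 30. With 1 baseline and 2 follow-ups, n = 33.
- *One reading per visit.* 1 + 5 + 2 gives n = 8.
- *Only the scheduled times named in Protocol 18.* Baseline, after session 5 and two follow-ups give n = 4.

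**Formula.** Let s = 1/n be the baseline share, R the true post-dose ratio, and k the baseline risk divided by the SHAM risk. Baseline risk is taken as the same in every round. Then

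observed ratio = (s·k + (1 − s)·R) / (s·k + (1 − s)).

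Example with n = 33, R = 2, k = 1: (1 + 32 × 2)/(1 + 32) = 65/33 = 1.97.

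**Observed ratio when R = 2** (R and k are assumptions)

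| n | baseline share | k = 0 | k = 0.5 | k = 1 | k = 2 |
|---|---|---|---|---|---|
| 33 | 3.0% | 2.00 | 1.98 | 1.97 | 1.94 |
| 8 | 12.5% | 2.00 | 1.93 | 1.88 | 1.78 |
| 4 | 25% | 2.00 | 1.86 | 1.75 | 1.60 |

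At k = 0 each rate is multiplied by 1 − s, so it falls by 3.0%, 12.5% or 25% of its value. With R = 1 the formula returns 1 for every n and k, so no false signal is created on average.

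**Scale against chance.** Assume 4% of readings are high under dAIH and 2% under SHAM, with 20 participants and 33 readings per round. There are two dAIH rounds and one SHAM round.

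- SHAM events: 20 × 33 × 0.02 = 13.2
- dAIH events: 2 × 20 × 33 × 0.04 = 52.8
- SE(log ratio) = √(1/13.2 + 1/52.8) = 0.308
- Rough 95% interval: 2.0 × exp(±1.96 × 0.308) = 1.09 to 3.66

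This ignores clustering of readings within participants, so the real interval is likely to be wider. A shift of 0.03 is small beside it.

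**The case against.** The strongest reply is that this does not matter, and most of it stands.

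- **Size.** On the most natural count the ratio moves from 2.00 to 1.97, in a descriptive summary with no test or stopping rule tied to it. The count may even be higher than 33. Protocol 11b has BP monitored through the 30-minute wait, and Protocol 18 has systolic pressure taken before, during and immediately after breathing. If that adds two readings per session, n = 43 and the ratio at k = 1 is 85/43 = 1.98. The n = 8 and n = 4 rows need readings of the text that it does not favour.
- **Few high baselines.** Hypertension is an exclusion in Protocol 10, so k may well be near 0, and nothing in the documents supports k = 2. Against this, Protocol 11d anticipates medication for systemic hypertension, so high baseline readings are not ruled out.
- **The text is only silent.** An analyst could treat baseline as a comparator, given the words on incidence and onset. This does not stand: the denominator is the total number of BP measurements, and baseline is a named occasion.
- **The cut-off is imperfect.** Breathing starts 30 minutes after the capsule, so day-1 readings in the wait would still count although they carry no AIH effect. That is true. But each intervention is a capsule plus a breathing session, and counting from the first component is the usual treatment-emergent rule. The dAIH side also pools caffeine and placebo rounds while the only SHAM round has caffeine, so the ratio is not a clean AIH effect either way. That is a separate limitation, which this change neither causes nor cures.

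**Conclusion.** The point holds and is of low priority. The stated rule lets a pre-treatment reading count towards each intervention's hypertension rate. The expected bias is towards 1: about 0.03 on a ratio of 2 when all session readings count and baseline risk equals SHAM risk, and up to 0.25 at that same risk if only the four scheduled readings count. These sizes rest on an assumed true ratio of 2, assumed values of k, equal baseline risk across rounds, and complete rounds. A round stopped early has fewer on-treatment readings, so its baseline would weigh more.

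The walking-speed analysis is untouched. Participant protection depends on the discontinuation rules in Protocol 11b and SAP 13, not on this rate.

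**What to change.** In Protocol 18, state that events and person-measures are counted only from the first capsule of each round, and that readings taken during sessions are included. Report baseline-visit readings over either BP threshold separately, by intervention. Do not drop a round because its baseline reading is high. The all-readings rate can stay as a supporting summary.

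The cost is a sentence or two of wording, using readings already planned. One reading per round leaves the rate, at most 20 × 3 × 1 = 60. All rounds and all on-treatment and follow-up readings remain, so the within-person comparison is kept.
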